The prosthesis-related quality of life is assessed during this first appointment, using domains “About the prosthesis” (question group 1 of the PEQ), “Specific Bodily Sensations” (group 2), “Ability to Move Around” (group 4), and “Satisfaction with particular Situations” (group 5). “Importance of different aspects” (group 7) is assessed as well, to provide insights for appropriate interpretation of responses. The PEQ contains a large number of questions that have been devised to cover all aspects of prosthesis-related quality of life. The explicit intention of the tool is to provide the option of customizing a questionnaire by selecting a subset of the PEQ questions, all of which are considered equivalent and are scored on an analog scale from 0 to 100. The PEQ is valid for lower-limb prosthesis users, has high internal consistency (Cronbach’s alpha = .73 – .89) and temporal stability over a mean retest period of 30 days (ICC = .79 – 90). The likewise administered two-minute walk test (2MWT) has well established psychometric properties in lower-limb prosthesis users. Of particular interest to the proposed study is the responsiveness of the 2MWT to rehabilitation in lower-limb prosthesis users. Significant increases in total distance were found from initial prosthesis fitting (baseline) to discharge from rehabilitation, and at a 3-month follow-up. A Stepwatch monitor (Modus Health, Washington, DC) is affixed to the ankle of the prosthesis and measure step counts over time.

This device has been utilized for a large number of research studies involving lower limb prosthetics and meets the specifications issued by the Department of Veterans Affairs regarding outcome assessment technology. Using the “Trex” evaluation algorithm, the device allows an assessment of user activity by considering ambulation energy, peak performance, and cadence variability indices.

In addition to determining liner sizes, subjects’ height, weight, age, and time since limb loss are recorded at the first appointment.

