Subjects are asked to continue their regular activities of daily life while wearing the new liner, and to make a note of any days during which the prosthesis could not be used due to residual limb health issues, as a redundancy to the step counter data. About every two weeks, a member of the research team will schedule a 5-minute appointment with the subject to read out Stepwatch data. Subjects are not required to come to the research site for the respective appointments, which may be scheduled at their homes or places of work according to subjects’ preferences. While the Stepwatch monitor can store up to 50 days of data, two-week-intervals have been chosen to mitigate the adverse effects of possible equipment malfunction or application errors. Any adverse events or other unsolicited reports will be recorded as they occur.

Every six weeks, appointments are scheduled to conduct the 2MWT, complete sections “About the prosthesis”, “Specific Bodily Sensations”, “Ability to Move Around”, “Satisfaction with particular Situations”, and “Importance of different aspects” of the PEQ, and read out step data.

At the 6-month appointment, after completing 2MWT and PEQ, subjects turn in their two study liners and receive two new liners, representing the respectively other variety. Following a short rest, subjects will complete the 2MWT and PEQ once more before the test day is concluded while wearing the new liner.

The 12-month appointment marks the end of the data collection for this study. Individuals blinded to liner type will perform all data collection.

Subjects receive a compensation of \$30 per site visit for a total compensation of \$270. This payment schedule is intended to reduce the occurrence of drop-outs.

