Patterns of association between descriptive measures (i.e., demographic and diagnosis characteristics) and intervention outcomes will be examined using paired t-tests, chi-square tests with Fisher's exact, correlation analyses (and regression analyses, as appropriate). From these analyses, critical demographic and clinical characteristics will be identified that will be controlled for in the statistical models and incorporated into the design of future controlled clinical studies. Data will be analyzed according to study group membership regardless of study completion. However, missing data patterns will be examined and reasons described for attrition and missing data because such patterns may be informative for identifying systematic biases in future studies. The Kolmogorov-Smirnov test will be used to verify the normality assumption and if it is violated appropriate transformations will be considered. Correction for multiple testing will be by adjusting p-values using the Benjamini-Hochberg method. Prior to formal statistical analysis, data will be compared across treatments to check if they are comparable. If differences exist, baseline demographic effects will be taken into account in mixed effects models. The correlation among repeated measures will be examined and adjusted appropriately such as unstructured, confound symmetry, or auto-regressive.

Outcome data are collected at baseline, 1.5-month, 3-month, 4.5-month, and 6 months and repeated at the 2nd half-year. The effect of intervention, time, and group\*time interactions will be evaluated. Baseline data for key variables will be compared between randomization groups, and if they are different, a random intercept mixed effect will be used. Mixed effects modeling techniques will be used for the repeated measures. Since mixed effects models do not assume a balanced design, subjects who do not have data (dropouts) on all 10 time points will still be

included in the analysis (intent to treat). It will be tested if scores for the intervention are significantly different from the control condition's scores.

Possible additional analyses include a more detailed investigation of prosthesis utilization over time by comparing seasons, months, weekdays, or hours of day within and across interventions. Furthermore, it may be possible to analyze covariates that predict prosthesis utilization, including anthropometric and demographic data.

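### The random intercept depends on a chance baseline difference between randomization groups; a crossover needs a subject effect in every case, with the remaining correlation fixed in advance

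*Combined protocol and SAP*

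**What the plan says.** Four statements under Statistical Plan and Data Analysis bear on the model for the repeated measurements.

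- The random intercept is conditional: "Baseline data for key variables will be compared between randomization groups, and if they are different, a random intercept mixed effect will be used". No test, threshold or list of key variables is given.
- The correlation structure is left open: "The correlation among repeated measures will be examined and adjusted appropriately such as unstructured, confound symmetry, or auto-regressive". The second term is evidently compound symmetry. No selection rule is stated.
- The model class is unconditional: "Mixed effects modeling techniques will be used for the repeated measures".
- The effects to be examined are "The effect of intervention, time, and" a group-by-time interaction. The comparison of interest is put this way: "It will be tested if scores for the intervention are significantly different from the" scores under control. Neither group nor time is defined.

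The section counts 10 time points, five in each half-year. Methods describes the 6-month visit, at which subjects are tested in the old liner and then change to the new one: "Following a short rest, subjects will complete the 2MWT and PEQ once more". The fifth and sixth measurements of 2MWT and PEQ therefore fall on the same day. For step data, Methods says: "About every two weeks, a member of the research team will schedule a 5-minute appointment with the subject to read out Stepwatch data".

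**The concern.** A random intercept represents stable differences between subjects, and hence the correlation among one subject's measurements. A difference between randomization groups at baseline concerns group means. After randomization it arises by chance, and its presence or absence carries no information about that correlation. In a crossover each subject is his or her own control, so the subject effect belongs in the model whether or not the sequences look balanced.

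If the trigger does not fire, the model rests on whichever residual structure is chosen after looking at the data. Two of the three named structures are incomplete when a subject effect and serial correlation are both present. Compound symmetry has no decay over time, and AR(1) has no lasting subject effect. The first makes the standard error of the liner effect too small; the second wastes information. Only the unstructured matrix covers both, and at 10 visits it has 10 × 11 / 2 = 55 covariance parameters for about 41 completers (50 minus 9).

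**Working it through.** **The plan's own figures.** The documents give no operating characteristics for the mixed model. Their only power figures are 85% with 50 subjects and 80% with 41, at effect size 0.47, one-sided, alpha not stated. A paired z calculation at one-sided 5% gives Φ(0.47√50 − 1.645) = Φ(1.678) = 95.3% and Φ(0.47√41 − 1.645) = Φ(1.364) = 91.4%. The stated figures are not reproduced. That is a separate matter, and nothing below depends on it.

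**Inputs.** From the documents: 10 visits, two sequences, 41 completers. Assumed: 21 and 20 per sequence, complete data, two-sided 5%, equally spaced visits, fixed effects for visit, sequence and liner, and an effect set to give 80% power under the true model. Also assumed are the subject share of variance (0.3 to 0.9) and the serial correlation ρ between adjacent visits (0 to 0.5). The PEQ ICC of .79-.90 is the only within-subject correlation given, and the PEQ is a secondary outcome.

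**Step 1: how often the trigger fires.** With a 5% test it fires by chance in 5% of trials for one variable. For five independent scores (2MWT and four PEQ ratings) the chance is 1 − 0.95^5 = 23%. In simulation it falls to about 15% when the scores correlate at 0.7.

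**Step 2: compound symmetry alone.** The liner effect comes from the within-subject difference of the two period means, so the subject share cancels. In units of the residual variance:

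- true variance: V = {2[5 + 2(4ρ + 3ρ² + 2ρ³ + ρ⁴)] − 2ρ(1 + ρ + ρ² + ρ³ + ρ⁴)²} / 25
- variance the model assumes: M = 0.4(1 − r), where r = Σ 2(10 − k)ρ^k / 90 over k = 1 to 9
- type I error: 2[1 − Φ(1.96 / √(V/M))]

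At ρ = 0.3: V = (16.128 − 1.219) / 25 = 0.596, r = 0.0816, M = 0.367, V/M = 1.624, and 1.96 / 1.274 = 1.538, which gives 12.4%.

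| ρ | V | M | V/M | Type I error |
|---|---|---|---|---|
| 0 | 0.400 | 0.400 | 1.000 | 5.0% |
| 0.1 | 0.459 | 0.391 | 1.174 | 7.0% |
| 0.2 | 0.525 | 0.381 | 1.380 | 9.5% |
| 0.3 | 0.596 | 0.367 | 1.624 | 12.4% |
| 0.5 | 0.740 | 0.329 | 2.250 | 19.1% |

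Compound symmetry is the same model as a random intercept with independent residuals, so adding an intercept alone does not cure this.

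**Step 3: AR(1) without a subject intercept.** In large samples the fitted lag-one correlation is the share plus (1 − share) × ρ. At ρ = 0.5 that is 0.65 to 0.95. Power is then 71%, 65%, 61% and 59% at shares 0.3, 0.5, 0.7 and 0.9, where the true model has 80%. Type I error stays at or below 5%.

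**Step 4: choosing between these two by likelihood** (1000 simulated trials per setting).

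- ρ = 0: AR(1) is never picked; power 79-81%, type I error 4-5%.
- ρ = 0.1 and 0.2: type I error 7-8% and 9-10%.
- ρ = 0.3: type I error 11-12% at shares 0.5-0.9; power 70% at share 0.3.
- ρ = 0.5: AR(1) is picked in 85-99% of trials; power 71.1%, 66.7%, 64.3% and 62.8% by share.
- Intercept plus AR(1), fixed in advance, in all settings: power 77-82%, type I error 4-6%.

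**Step 5: the trigger's own contribution.** At ρ = 0.5, letting a difference on one baseline score add the intercept gives power of 71.0%, 67.3%, 65.1% and 63.4%. The changes are −0.1, +0.6, +0.8 and +0.6 points, against a shortfall from 80% of 8.9 to 17.2 points.

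**Step 6: same-day pair.** Suppose the two 6-month measurements share their serial term, with measurement error assumed to be 0.3 of the residual variance and serial correlation 0.3-0.7 per six weeks. Intercept plus AR(1) in visit order then has type I error 2-4% and power 57-66%; the likelihood choice has 2-11% and 50-69%. With lag measured in months and no measurement-error term, the matrix has rank 9 of 10 and cannot be used.

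**Step 7: a simpler alternative.** A two-sample t-test between sequences on within-subject differences of period means holds 5% for complete normal data whatever the common serial correlation. Its power is 75-78% at ρ = 0-0.3, 69% at 0.5, and 57-62% in the same-day setting.

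**The case against.** The strongest reply is that the section already deals with within-subject correlation. Mixed models are promised without condition, the correlation is to be examined, and compound symmetry is itself a random-intercept model. This stands. A reader might infer from the conditional sentence that correlation would be ignored whenever the groups look alike, with a severe loss of power; the documents do not support that.

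A second reply is that the simulated rule is narrower than the plan's. The list of structures is introduced as examples, so it would allow an intercept with a serial residual. It also names the unstructured matrix, which covers the case and was not simulated. This stands too: the figures show what can happen under two of the permitted choices, and do not predict what the statistician would do.

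Third, a reader might apply the argument to 26 two-week step intervals, where an unstructured matrix has 26 × 27 / 2 = 351 parameters and the simulated power losses are larger. Those results are illustrative only. Methods gives the two-week read-out as a safeguard against equipment failure and misuse, and no section makes two weeks the unit of analysis. If steps are totalled per half-year there are two values per subject, compound symmetry and AR(1) coincide, and the choice costs nothing.

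Fourth, AR(1) in visit order is not clearly better for 2MWT and PEQ, because of the same-day pair. It controls false positives but may be conservative, so it should not be presented as the only sound remedy.

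Finally, a reader might conclude from the undefined group-by-time term that the liner effect cannot be estimated. If group means sequence and time means visit or period, a separate liner coefficient is redundant. A contrast of cell means still recovers the comparison the plan states, so this needs definition only.

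**Conclusion.** The conditional rule is wrong in principle, and that conclusion needs no assumed figure. Its direct numerical effect is small. The material risk is the structure left open once the subject effect is not fixed: moderately inflated type I error if compound symmetry is used alone, or lost power if AR(1) is used alone. Both arise only if residuals are serially correlated, and the documents give no correlation for step count or days of use. All shares and serial correlations are assumptions, and the calculations use 41 completers although the plan also keeps dropouts in the analysis. A separate check, one-sided at 5% with 25 per sequence and subject share 0.79, shows the same pattern. Compound symmetry gives 10.1% type I error at serial correlation 0.3. AR(1) alone has 53% power there, where the effect was set for about 85%. Confidence is high that the trigger should go and moderate about the size of the harm.

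**What to change.** Under Statistical Plan and Data Analysis:

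1. Delete the sentence that makes the random intercept depend on baseline comparison, and state that a subject random intercept is always included.
2. State in advance one rule for the remaining within-subject correlation that keeps the liner test valid. Sound options are an intercept plus a serial residual, an unstructured matrix with a small-sample correction, or a comparison of within-subject period means.
3. For 2MWT and PEQ, say how the chosen rule treats the two measurements on the 6-month day. If lag in months is used, a measurement-error term is required.
4. For step data, name the interval analysed, since this settles whether the choice matters.
5. Define group and time, and name the liner term as the primary test, for example in a model with visit, sequence and liner.

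The cost is wording and, with a serial residual, one or two more covariance parameters. No new data are needed. The downside is possibly some power lost to a conservative structure, most likely for 2MWT and PEQ.

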### **List of Abbreviations**

2MWT – Two Minute Walk Test

HIPAA – Health Insurance Portability and Accountability Act of 1996

ICC – Intraclass correlation coefficient

PCM – Phase Change Material

PEQ – Prosthesis Evaluation Questionnaire

SPIRIT – Standard Protocol Items: Recommendations for Interventional Trials

